- Chronic clinical conditions will be aggregated using the Healthcare Cost and Utilization Project's Clinical Classification Software, which reduces all ICD-9/10 codes to 285 clinically meaningful groups⁴². The CCS has been updated to include ICD-10, which is important, as this project will span ICD-9 and 10 eras.
- Medication exposures will be aggregated using the PCORNet⁴³ instantiation of the RxNorm controlled vocabulary⁴⁴ and leveraging this vocabulary to the Anatomical Therapeutic Chemical (ATC) Level 4 groupings, which are clinically relevant drug classes.

Some co-variates may not be ascertainable in some participating sites' PCORNet CDM instances, and this will be explored and reported. Each of the outcomes, exposures, and covariates will be analyzed for counts in each site and a summarization and report will be provided to characterize the data at each site. Stratified reporting of those receiving surgery for SUI with mesh and those without mesh will be performed.

Next, if the characterization of the data is sufficient for the task, we will pursue a Cox proportional hazards model analysis, with each of the outcomes assessed from the time of the surgery as a time-to-event. We will censor the time-to-event analysis with death or loss to follow-up, defined as a time period

Version 2.0

[15 July 2020]

>2 years from last applicable encounter of primary care, Obstetrics & Gynecology, or Urology. The models will be executed at each institutional separately using LASSO Cox to determine the consistently included covariates in each institution⁴⁵. We will then use the final variable list and utilize the method described by Lu and colleagues that uses a distributed analysis approach to obtain an exact model solution without sharing case level data (only intermediate and aggregate model coefficients and matrices)⁴⁶.

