		 Mesh exposure and erosion (ICD9/10 629.31, 629.32/T83.711, T83.721) Urinary Retention (CPT Code 53500, ICD 9/10 788.20, 788.21/R33.0, R33.8-R33.9) Urgency of urination (ICD9/10 788.63/R39.15) Urge incontinence (ICD9/10 788.31/N39.41) Bowel injury (ICD9/10 569.83/S36) Bladder/urethral injury (ICD9/10 596.6,867.0/S37) Infection (ICD9/10 686.9,998.5,999.3,998.51,998.59/T81) Retropubic hematoma (ICD 9/10 568.81,,568.81,459.0/K66.1) Retopubic hematoma (ICD 9/10 568.81,,568.81,459.0/K66.1) Retopubic hematoma (ICD 9/10 568.81,568.81,459.0/K66.1) Bulking Injection CPT 51715, ICD 9/10 59.72/ PCS 3E0K3GC Laparoscopic Retropubic Urethropexy CPT 51990, 51992, 51999 Abdominal Retropubic Urethropexy CPT 51840,51841 Needle Bladder Neck Suspension CPT 51845 Kelly plication CPT 57220 Cystourethroplasty CPT 51800 Subtypes: Stress incontinence, female/mixed incontinence (ICD9/10 625.6,788.33/N39.46) Stress incontinence (female) (male)(ICD10 CM N39.3) 		
Outcome	Mesh Removal	 General, CPT 57287-Removal or revision of sling for stress incontinence (fascia or synthetic) ***some erosions managed surgically may have been coded by a different CPT (i.e. 57295 revise vaginal graft via vaginal approach) and not CPT 57287, which indicates a sling revision/removal. 	Yes	Possible Options: (a surgery for any kind of mid-urethral sling, urethral bulking agent, black neck pubovaginal sling (autologous or allograft), or revision for mesh exposure). Represented as a Date, allows time-to-event analysis.
Outcome	Post-Procedural Pain	?, mix of vital sign (pain score >3 of 10 on vital sign data) and likely free text. Also, diagnosis codes related to abd/pelvic pain (if prior pain free).	Some portion	Would have to exclude prior chronic pain or detect specific mention of new pain (free text). Could analyze group with no pre-surgical pain,

Protocol 1				[15 July 2020]
				otherwise probably beyond scope. Date/Time of first post- op occurrence.

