Outcome	Mesh Erosion	Admin Codes: ICD-9-CM codes for mesh erosion: 996.30, 996.39, 996.59, 996.60, 996.65, 996.69, 996.70, 996.76, 996.79, 939.0, 939.2, and 939.9 ICD 10 CM: T83.498A, T85.698A, T85.79XA, T83.598A, T85.79XA, T85.9XXA, T83.89XA, T85.898A, T19.0XXA, T19.2XXA, T19.9XXA Surgical Complications: ICD 9/10 629.31/T83.711 Erosion of implanted vaginal mesh ICD 9/10 629.32/T83.721S Exposure of implanted vaginal mesh ICD 9/10 996.76/T83.9 Complication of genitourinary device, implant or graft ICD9/10-PCS V58.2/30233N1, 30233P1, 30233H1 Blood transfusion ICD9/10 998.5/ T81.49XA, T81.40XS, T81.41, T81.43, T83.5, T83.6 Postoperative infection ICD 9/10 778.2/R33.9 Urinary retention		Capture as date/time Exclude 629.3- complication of implanted vaginal mesh and other prosthetic materials, 629.31- erosion of implanted vaginal mesh, or 629.32-exposure of implanted vaginal mesh because these ICD-9 were not released until 2011? ²⁸ SME determined that topical estrogen could be prescribed for other reasons
Outcome	Urethral fistula	Admin Codes ICD 9- 599.1 ICD 10-N36.0	Yes	Capture as date/time
Covariate	Prior Abdominal Surgery Or Pelvic Radiation	Admin Codes: Personal history of irradiation-V15.3/Z92.3, Irradiation cystitis- N30.4	Yes	Yes/No
	Therapy	CPT/ICD 9/ICD 10 for prior abdominal surgery:		

Protocol 1		[15 July 2020]
	Hysterectomy: 00846, 00855, 00944, 01962,	
	01963, 01969,45126, 51597, 51925, 56308,	
	58150, 58152, 58180, 58200, 58205, 58210,	
	58240, 58260, 58262, 58263, 58265, 58267,	
	58270, 58275, 58280,	
	58285, 58290, 58291, 58292, 58293,	
	58294, 58541, 58542, 58543, 58544,	
	58548, 58550, 58552, 58553, 58554,	
	58570, 58571, 58572, 58573, 58575,	
	58951, 58953, 58954, 59135,	
	59525, 59560, 59561, 59580, 59581	
	/68.9/290.711	
	Cesarean section: 00850, 59500, 59501,	
	59520, 59521, 59540, 59541/649.81/075.82	
	Appendectomy: 44950, 44955, 44960,	
	44970, 49315, 56315/V45.79/Z90.89	
	Hernia repair: 49505, 49507, 49520,	
	49521, 49525, 49550, 49553, 49555,	
	49557, 49560, 49561, 49565, 49566,	
	49570, 49572, 49585, 49587, 49590,	
	49650, 49651, 49652, 49653, 49654,	
	49655, 49656, 49657, 49659/53.5/0WQF0ZZ,	
	0WQF3ZZ, 0WQF4ZZ	
	Cholecystectomy: 47562, 47563, 47564, 47600,	
	47605, 47610, 47612, 47620/51.0-	
	51.04/0FT40ZZ	
	51.04/01 14022	
	Colectomy: 44139, 44140, 44204, 44205, 44206,	
	44141, 44143, 44144, 44145, 44146, 44147,	
	44150, 44151, 44157, 44158, 44160,44320,	
	44322, 44799, 45110, 45111, 45112, 45113,	

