Outcome	Perforation (vagina, urinary	 Admin Codes & Free Text (Possibly) Erosion of other implanted mesh to organ or tissue ICD10CM-T83.712 Erosion of implanted urethral mesh to surrounding organ or tissue, initial encounter-T83.712A 	Yes	complication, capture as
Outcome	Perforation (vagina, urinary	 Admin Codes & Free Text (Possibly) Erosion of other implanted mesh to organ or tissue ICD10CM-T83.712 Erosion of implanted urethral mesh to surrounding organ or tissue, initial encounter-T83.712A Erosion of implanted urethral mesh to 	Yes	complication, capture as
Outcome	Perforation (vagina, urinary	 Admin Codes & Free Text (Possibly) Erosion of other implanted mesh to organ or tissue ICD10CM-T83.712 Erosion of implanted urethral mesh to surrounding organ or tissue, initial encounter-T83.712A Erosion of implanted urethral mesh to surrounding organ or tissue 	Yes	complication, capture as
Outcome	Perforation (vagina, urinary	 Admin Codes & Free Text (Possibly) Erosion of other implanted mesh to organ or tissue ICD10CM-T83.712 Erosion of implanted urethral mesh to surrounding organ or tissue, initial encounter-T83.712A Erosion of implanted urethral mesh to surrounding organ or tissue subsequent encounter-T83.712D 	Yes	complication, capture as
Outcome	Perforation (vagina, urinary	 Admin Codes & Free Text (Possibly) Erosion of other implanted mesh to organ or tissue ICD10CM-T83.712 Erosion of implanted urethral mesh to surrounding organ or tissue, initial encounter-T83.712A Erosion of implanted urethral mesh to surrounding organ or tissue 	Yes	complication, capture as
Outcome	Perforation (vagina, urinary	 Admin Codes & Free Text (Possibly) Erosion of other implanted mesh to organ or tissue ICD10CM-T83.712 Erosion of implanted urethral mesh to surrounding organ or tissue, initial encounter-T83.712A Erosion of implanted urethral mesh to surrounding organ or tissue subsequent encounter-T83.712D 	Yes	complication, capture as
Outcome	Perforation (vagina, urinary	 Admin Codes & Free Text (Possibly) Erosion of other implanted mesh to organ or tissue ICD10CM-T83.712 Erosion of implanted urethral mesh to surrounding organ or tissue, initial encounter-T83.712A Erosion of implanted urethral mesh to surrounding organ or tissue subsequent encounter-T83.712D Erosion of implanted urethral mesh to surrounding organ or tissue subsequent encounter-T83.712D 	Yes	complication, capture as

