Outcome	Perforation (vagina, urinary	 Admin Codes & Free Text (Possibly) Erosion of other implanted mesh to organ or tissue ICD10CM-T83.712 Erosion of implanted urethral mesh to surrounding organ or tissue, initial encounter-T83.712A Erosion of implanted urethral mesh to surrounding organ or tissue subsequent encounter-T83.712D Erosion of implanted urethral mesh to surrounding organ or tissue subsequent encounter-T83.712D Erosion of implanted urethral mesh to surrounding organ or tissue, sequela- 	Yes	complication, capture as
Outcome	Perforation (vagina, urinary	 Admin Codes & Free Text (Possibly) Erosion of other implanted mesh to organ or tissue ICD10CM-T83.712 Erosion of implanted urethral mesh to surrounding organ or tissue, initial encounter-T83.712A Erosion of implanted urethral mesh to surrounding organ or tissue subsequent encounter-T83.712D Erosion of implanted urethral mesh to surrounding organ or tissue, subsequent encounter-T83.712D Erosion of implanted urethral mesh to surrounding organ or tissue, sequela-T83.712S 	Yes	complication, capture as
Outcome	Perforation (vagina, urinary	 Admin Codes & Free Text (Possibly) Erosion of other implanted mesh to organ or tissue ICD10CM-T83.712 Erosion of implanted urethral mesh to surrounding organ or tissue, initial encounter-T83.712A Erosion of implanted urethral mesh to surrounding organ or tissue subsequent encounter-T83.712D Erosion of implanted urethral mesh to surrounding organ or tissue subsequent encounter-T83.712D Erosion of implanted urethral mesh to surrounding organ or tissue, sequela-T83.712S Exposure of implanted urethral mesh into urethra ICD10-T83.722 	Yes	complication, capture as
Outcome	Perforation (vagina, urinary	 Admin Codes & Free Text (Possibly) Erosion of other implanted mesh to organ or tissue ICD10CM-T83.712 Erosion of implanted urethral mesh to surrounding organ or tissue, initial encounter-T83.712A Erosion of implanted urethral mesh to surrounding organ or tissue subsequent encounter-T83.712D Erosion of implanted urethral mesh to surrounding organ or tissue subsequent encounter-T83.712D Erosion of implanted urethral mesh to surrounding organ or tissue, sequela-T83.712S Exposure of implanted urethral mesh into urethra ICD10-T83.722 Exposure of implanted urethral mesh 	Yes	complication, capture as

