	Perforation (vagina, urinary tract)	 Admin Codes & Free Text (Possibly) Erosion of other implanted mesh to organ or tissue ICD10CM-T83.712 Erosion of implanted urethral mesh to surrounding organ or tissue, initial encounter-T83.712A Erosion of implanted urethral mesh to surrounding organ or tissue subsequent encounter-T83.712D Erosion of implanted urethral mesh to surrounding organ or tissue, sequela-T83.712S Exposure of implanted urethral mesh into urethra ICD10-T83.722 Exposure of implanted urethral mesh into urethra, initial encounter T83.722A Exposure of implanted urethral mesh into urethra, subsequent encounter T83.722D Exposure of implanted urethral mesh into urethra, subsequent encounter T83.722D Exposure of implanted urethral mesh into urethra, subsequent encounter T83.722D Exposure of implanted urethral mesh into urethra, subsequent encounter T83.722D 	Yes	complication, capture as
Outcome	Perforation (vagina, urinary tract)	 Admin Codes & Free Text (Possibly) Erosion of other implanted mesh to organ or tissue ICD10CM-T83.712 Erosion of implanted urethral mesh to surrounding organ or tissue, initial encounter-T83.712A Erosion of implanted urethral mesh to surrounding organ or tissue subsequent encounter-T83.712D Erosion of implanted urethral mesh to surrounding organ or tissue, sequela-T83.712S Exposure of implanted urethral mesh into urethra ICD10-T83.722 Exposure of implanted urethral mesh into urethra, initial encounter T83.722A Exposure of implanted urethral mesh into urethra, subsequent encounter T83.722D Exposure of implanted urethral mesh into urethra, subsequent encounter T83.722D Exposure of implanted urethral mesh into urethra, subsequent encounter T83.722D Exposure of implanted urethral mesh into urethra, subsequent encounter T83.722D Exposure of implanted urethral mesh into urethra, subsequent encounter T83.722D Exposure of implanted urethral mesh into urethra, subsequent encounter T83.722D Exposure of implanted urethral mesh into urethra, sequela-T83.722S 	Yes	complication, capture as

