	788.39/N39.4 Other urinary incontinence
Prolapse	618.01/N81.11 Cystocele, midline
	618.02/N81.12 Cystocele, lateral
	618.03/N81.0 Urethrocele
	618.81/N81.82 Incompetence or weakening of pubocervical fascia
	618.1 Uterine prolapse without mention of vaginal wall prolapse
	618.2/N81.2 Uterovaginal prolapse, incomplete
	618.3/N81.3 Uterovaginal prolapse, complete
	618.4/N81.4 Uterovaginal prolapse, unspecified
	618.5/N99.3 Prolapse of vaginal vault after hysterectomy
	618.6/N81.5 Vaginal enterocele, congenital or acquired
	618.94/N81.85 Cervical stump prolapse
	618.04/N81.6 Rectocele
	618.05/N81.81 Perineocele
	618.82/N81.83 Incompetence or weakening of rectovaginal fascia
	618.00/N81.4Unspecified prolapse of vaginal walls
	618.09/N81.89 Other prolapse of the vaginal walls without mention of utering
	prolapse

	618.7/N88.1 Old laceration of muscles of pelvic floor
	618.83/N81.84 Pelvic muscle wasting
	618.89/N81.89 Other specified genital prolapse
	618.9/N81.9 Unspecified genital prolapse
Surgical Complications	629.31/T83.711 Erosion of implanted vaginal mesh
	629.32/T83.721 Exposure of implanted vaginal mesh
	996.76/T83.9 Complication of genitourinary device, implant or graft
	V58.2 Blood transfusion
	998.5 Postoperative infection
	778.2/R33.9 Urinary retention

Procedures

SUI Procedures – Sling	59.4/ OTSC4ZZ Suprapubic sling operation 59.79/ OTQD3ZZ Pubovaginal sling; Anterior urethropexy; Repair of stress incontinence NOS
SUI Procedures - Burch	59.5/ 0TSD4ZZ, 0TSD0ZZ Retropubic urethral suspension (Burch)
SUI Procedures - Other	59.6/ OTSC4ZZ, OTSCOZZ Paraurethral suspension
Soff foreduces of the	59.71/ OTUCOKZ Levator muscle operation for urethrovesical suspension
	59.72/ 3E0K4GC Injection of implant into urethra and/or bladder neck
Anterior Repair	70.51/ 0JQC0ZZ, 0JQC3ZZ Repair of cystocele
	70.54/ 0JUC07Z, 0JUC0JZ, 0JUC0KZ, 0JUC37Z, 0JUC3JZ, 0JUC3KZ Repair of
	cystocele with graft or prosthesis
Posterior Repair	70.52/ 0JQC0ZZ, 0JQC3ZZ Repair of rectocele

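### The Mesh Erosion row lists vaginal-mesh exposure only under the sequela code T83.721S, contrary to the rest of the appendix, so first exposure diagnoses in ICD-10 data may be missed or dated late

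*Protocol*

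**What the plan says.** All code lists here are in Protocol Section 13, Appendices.

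- **Mesh Erosion row.** A first block lists ICD-9-CM codes for mesh erosion and a set of ICD-10-CM codes. A second block, labelled Surgical Complications, contains "ICD 9/10 629.31/T83.711 Erosion of implanted vaginal mesh" and "ICD 9/10 629.32/T83.721S Exposure of implanted vaginal mesh". It continues with a general genitourinary device-complication code, blood transfusion, postoperative infection and urinary retention. The outcome is captured as date/time. A note in the row asks, with a question mark, whether 629.3, 629.31 and 629.32 should be excluded because of when those ICD-9 codes were released.
- **Re-Operation row, subtypes.** The same diagnosis has no suffix: "Mesh exposure and erosion (ICD9/10 629.31, 629.32/T83.711, T83.721".
- **Diagnosis list at the end of the appendix, Surgical Complications.** Again no suffix: "629.32/T83.721 Exposure of implanted vaginal mesh".
- **Organ Mesh Perforation row.** The sister codes are spelled out by suffix, for example "surrounding organ or tissue, initial encounter-T83.712A", "Erosion of implanted urethral mesh to surrounding organ or tissue, sequela-T83.712S" and "Exposure of implanted urethral mesh into urethra, sequela-T83.722S".

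Section 4 says that "this project will span ICD-9 and 10 eras". Mesh erosion is named as an outcome in the synopsis and in the second aim of Section 3. Section 7 does not list it as a separate primary outcome.

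**The concern.** By the document's own key, the Mesh Erosion row accepts vaginal-mesh exposure in ICD-10 data only when it is coded as a sequela. A first diagnosis would carry the initial-encounter suffix, and the row has no such code for exposure.

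The outcome is a dated event, so two things can go wrong. A woman whose exposure is coded only as A or D yields no event from this code. A woman coded A first and S later yields an event at the S date, which can move it across the 1-year or 2-year boundary that separates mid-term from long-term outcomes.

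The appendix also becomes inconsistent across outcomes. If the stem in the Re-Operation row is read as a prefix, T83.721A labels a re-operation as due to exposure, yet the Mesh Erosion row does not recognise that code.

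Section 6 has one site write the transformation code for all five, so an error in the list would reach every site.

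**Working it through.** The protocol states no expected erosion rate, event count or sample size for this outcome, so there is no figure to reproduce. The check is a comparison of code lists.

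**Step 1. Match possible records against the ICD-10 codes in the Mesh Erosion row.** The appendix states no matching rule, so both exact and prefix matching were tried. The last two columns replace T83.721S with T83.721.

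| Code on the record | Exact, as written | Prefix, as written | Exact, with T83.721 | Prefix, with T83.721 |
|---|---|---|---|---|
| T83.711A | no | yes | no | yes |
| T83.721A | no | no | no | yes |
| T83.721D | no | no | no | yes |
| T83.721S | yes | yes | no | yes |

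As written, T83.721A and T83.721D are lost under either rule, because T83.721S is not the beginning of either. Swapping in the stem without a stated prefix rule does not help: under exact matching the bare stem finds none of the three. The stem T83.711 has the same weakness.

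**Step 2. Slip or choice?** The Surgical Complications entries in the row follow the diagnosis list at the end of the appendix in the same order: 629.31, 629.32, 996.76, V58.2, 998.5, 778.2. For exposure, the only difference is the added S. Every code in the row's first ICD-10 list ends in A, so that block targets initial encounters. No reason is given for accepting only sequelae of exposure. One infection code in the row, T81.40XS, also ends in S, and it too has no stated reason.

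**Step 3. Can the loss be sized?** Considering this defect alone, the fraction of erosion/exposure events lost is

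loss = w × e × (1 − k),

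where w is the share of events falling in ICD-10 data, e the share first coded as vaginal-mesh exposure, and k the share also caught by another listed code. The protocol gives none of the three. Purely as assumptions:

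- w = 0.3, e = 0.1, k = 0.5 gives 0.3 × 0.1 × 0.5 = 0.015.
- w = 1, e = 0.8, k = 0 gives 1 × 0.8 × 1 = 0.80.

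A range from 1.5% to 80% is not an estimate. It shows only that the document cannot settle the size.

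**Step 4. Can the net direction be settled?** If the whole row defines the outcome, it also counts urinary retention (R33.9), transfusion and infection. Section 1.1 cites voiding dysfunction of 3–30% after retropubic slings, against 1.6% for erosions needing intervention. Voiding dysfunction is not the same as an R33.9 code, and the 1.6% is not a rate beyond 1 year. Even so, the comparison shows that false positives could exceed the true events, so the net sign is unknown.

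**Step 5. Would the planned checks find it?** Each site reviews 50 to 100 charts. At the cited 1.6%, that is 50 × 0.016 = 0.8 to 100 × 0.016 = 1.6 erosion cases per site. The comparison with the curated single-site series covers 2010–2012 (Sections 4 and 6). If those years were coded in ICD-9, which is an assumption because the protocol gives no switch date, that comparison cannot exercise an ICD-10 code.

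**The case against.** A reader might infer that the reported mid- and long-term erosion rates will be too low, and by a quotable percentage. The documents do not support this, for four reasons.

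- **Other codes in the row push the other way.** Retention, transfusion and infection would count as erosion if the whole row is used. This stands. It does not bring back missed exposures, though; it is a second problem in the same row.
- **The row may not be meant as one list.** T83.711 and T83.721S appear only under the Surgical Complications label. If the first block alone defines erosion, no T83.711 or T83.721 code counts and the suffix is not the cause of any loss. This stands as a condition on the finding. On that reading, however, both explicitly named vaginal-mesh diagnoses fall outside the outcome, so the row still needs clarifying.
- **The ICD-9 side is open.** The note about excluding 629.31 and 629.32 means that an ICD-9 exposure may not count either, so a contrast between the two eras for this code pair cannot be taken as given. The note does not touch the ICD-10 codes.
- **Overlap is unknown.** The first block holds ten distinct broad device-complication codes, and T83.9 is also in the row. Some exposures may be caught through these.

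A reader might also infer that a primary outcome is compromised. Section 7 counts revision for mesh exposure under re-operation, and the Re-Operation row uses T83.721 without a suffix. The S in the Mesh Erosion row does not affect that outcome.

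**Conclusion.** The point holds as a wrong code in an outcome definition. The Mesh Erosion row restricts ICD-10 vaginal-mesh exposure to its sequela, in conflict with two other places in the same appendix. Provided that the row's Surgical Complications codes count toward the outcome, first exposure diagnoses coded A or D are not captured by this code, or are dated late when an S code follows. Taken alone, the defect can only lose or delay exposure events.

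No size can be attached. The ICD-10 share of events, the share coded as exposure and the overlap with other listed codes are all absent from the protocol, and the net direction of error in the reported erosion rate cannot be determined.

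The row should be corrected before the query code is distributed. The weight is moderate: mesh erosion is named in the synopsis and in Section 3, but it is not a separately listed primary outcome in Section 7.

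**What to change.** In the Mesh Erosion row:

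1. Replace T83.721S with T83.721 and state that it is matched as a prefix, or list T83.721A, T83.721D and T83.721S in full.
2. Apply the same rule to the stem T83.711. The Re-Operation row and the closing diagnosis list give bare stems with no matching rule, so one sentence covering the whole appendix is best.
3. State that these vaginal-mesh erosion and exposure codes count toward the mesh erosion outcome. Say also whether the other codes under Surgical Complications (retention, transfusion, infection) do.
4. Date the event at the first qualifying post-operative code, whatever its suffix, so that a woman with only an S code still has an event date.
5. Settle the open question on excluding 629.31 and 629.32 at the same time, so that the ICD-9 and ICD-10 definitions correspond.

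The cost is an edit to one row, one sentence on matching and the corresponding lines of query code. No new data are needed.

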3. STUDY OBJECTIVES

There remains uncertainty with regards to longer term outcomes among women receiving mesh slings for stress urinary incontinence, and this project seeks to address knowledge gaps for long term outcomes among mesh implantations by leveraging electronic health record data across 5 participating health systems.

Specific Aims: This project seeks to provide a proof of concept for post-market medical device surveillance by assessing the capacity of routinely collected electronic health record data to evaluate the long-term adverse outcomes related to synthetic surgical mesh implantation for stress urinary incontinence.

In pursuit of this goal, this project will:

- 1) Assess data element availability among key covariates and exposures among patients undergoing surgery for stress urinary incontinence,
- 2) If data are available, to assess rates of outcomes of mesh erosion, re-operation for SUI, reoperation for mesh revision or removal, chronic pain either as a new or worsening pain or requiring re-operation and voiding symptoms either as a new symptom or requiring reoperation, each with extended surveillance windows after surgery.
- 3) Specifically, this project will evaluate mid-term (>1 year) and long-term (>2 years) adverse events following synthetic surgical mesh implantation (mid-urethral slings) for female SUI.
- 4) Lastly, if the data quality and volume are sufficient, we will develop a risk prediction model for the risk of the each of the outcomes stated above among patients receiving mesh for SUI.

In summary, this project seeks to better understand the safety of mesh used for stress urinary incontinence by leveraging electronic health record data. The FDA intends on incorporating these data into its growing portfolio of evidence in order to help support regulatory decision making on level of risk

for these procedures and recommendations around use of mesh for this indication. This study has the potential to increase medical knowledge regarding these devices.

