	45114, 45119, 45120, 45121, 45123, 44204,	
	44205, 44206, 442Ø7, 442Ø8, 4421Ø, 44211,	
	44212, 44213, 44238, 45395, 45397/45.8, 45.81,	
	45.82, 45.83/0DTE4ZZ, 0DTE0ZZ, 0DTE7ZZ,	
	ODTE8ZZ	
	Lysis of abdominal adhesions: 44108, 44005,	
	58660, 58740, 53500/ 54.5, 54.51,	
	54.59/0DN84ZZ, 0DNE4ZZ, 0DNJ4ZZ, 0DNU4ZZ,	
	ODNV4ZZ, ODNW4ZZ, OFN04ZZ, OFN44ZZ,	
	OFN48ZZ OFN54ZZ, OFN64ZZ, OFN74ZZ, OFN84ZZ,	
	OFN94ZZ, OFNG8ZZ	
	Oophorectomy- 58661, 49321-51,	
	58940/V45.77/ Z90.722, Z90.721	
	555 10, 145.11, 250.122, 250.121	
	Cystocele and rectocele repair- 57260-51, 57282,	
	57267, 57270, 61809, 57240/70.50/ 0JQC0ZZ,	
	0JQC3ZZ	

Protocol 1			•	[15 July 2020]
		Gastrectomy- 43631, 43632, 43633,		
		43634/V45.75/Z90.3		
		Hystorestemy ⁵⁴ abdominal and vaginal		
		Hysterectomy ⁵⁴ , abdominal and vaginal C section		
		Appendectomy		
		Hernia repair		
		Cholecystectomy		
		Colectomy or colorectal resection		
		Excision, lysis peritoneal adhesions		
		Oophorectomy, unilateral and bilateral		
		Repair of cystocele and rectocele, obliteration of		
		vaginal vault		
		Gastrectomy		
		Other		
Outcome	Surgical Site Infection	Admin Codes & Free Text	Partially	Capture as date/time
		Pelvic, perineal abscess, or infection due to		Lahey Question:
		internal prosthetic device, implant and graft		Can antibiotic use in
		Infection due to implant:		within X days be a proxy
		996.69/T85.79XA		for SSI?
		Pelvic abscess ICD9/10:567.22/K65.1		
		614.3/N73.0		
		614.9 or 616.9/N73.9		
		614.4/N73.1		
		614.5/N73.5, N73.3		
		014.5/10/5.5/10/5.5		
		Perineal abscess ICD9/10:		
Outcome	Organ Mesh	682.2/L02.215 Admin Codes & Free Text (Possibly)	Vec	Direct surgical
Outcome	Organ Mesh	Admin Codes & Free Text (Possibly)	Yes	Direct surgical
Outcome	Perforation	Admin Codes & Free Text (Possibly) • Erosion of other implanted mesh to	Yes	complication, capture as
Outcome	Perforation (vagina, urinary	Admin Codes & Free Text (Possibly) • Erosion of other implanted mesh to organ or tissue ICD10CM-T83.712	Yes	_
Outcome	Perforation	Admin Codes & Free Text (Possibly) Erosion of other implanted mesh to organ or tissue ICD10CM-T83.712 Erosion of implanted urethral mesh to 	Yes	complication, capture as
Outcome	Perforation (vagina, urinary	 Admin Codes & Free Text (Possibly) Erosion of other implanted mesh to organ or tissue ICD10CM-T83.712 Erosion of implanted urethral mesh to surrounding organ or tissue, initial 	Yes	complication, capture as

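### The Mesh Erosion code list mixes erosion with general surgical complications and leaves urethral-mesh erosion to another outcome, so it is not a valid definition as written

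*Protocol*

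**What the plan says.** Aim 2 (Section 3) sets out to "assess rates of outcomes of mesh erosion, re-operation for SUI, reoperation for mesh revision or removal". The only code definition of erosion as an outcome in its own right is the Mesh Erosion row of the data collection table in Section 13.

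That row has one definition cell holding two lists. The first opens with "ICD-9-CM codes for mesh erosion: 996.30, 996.39, 996.59, 996.60" and continues with further ICD-9 device and foreign-body codes and an ICD-10 list. The second begins where the first ends: "T19.9XXA Surgical Complications: ICD 9/10 629.31/T83.711 Erosion of implanted vaginal mesh". It goes on with "ICD 9/10 629.32/T83.721S Exposure of implanted vaginal mesh", a general genitourinary device complication code (996.76/T83.9), and then "30233H1 Blood transfusion ICD9/10 998.5/ T81.49XA, T81.40XS, T81.41, T81.43, T83.5, T83.6 Postoperative infection ICD 9/10 778.2/R33.9 Urinary retention". No rule says which of these codes make an erosion.

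The row's notes ask whether the 629.3x codes should be excluded "because these ICD-9 were not released until 2011". The sentence ends in a question mark and is not resolved.

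The codes labelled urethral mesh stand in a different row, Organ Mesh Perforation, for example "Exposure of implanted urethral mesh into urethra ICD10-T83.722". The Surgical Site Infection row lists "996.69/T85.79XA", a pair that also appears in the first erosion list.

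Section 7 lists three primary outcomes: re-operation or mesh removal, chronic pain, and voiding symptoms. Mesh erosion is not among them.

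**The concern.** A site programmer who implements the row as it stands would flag an erosion when a woman is transfused, has a postoperative infection or is coded with urinary retention. Section 4 evaluates the same outcomes in women operated on without mesh, and Section 9.1 reports the two groups side by side. The row could therefore produce mesh erosions in women who have no mesh, and the indirect comparison would show them.

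The error also runs the other way. The device under study is a urethral sling, but a record carrying only a code labelled urethral-mesh erosion or exposure would not meet the row.

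Outcomes are analysed as time from surgery. If the first qualifying code sets the event date, an early retention or transfusion code would replace a later true erosion. Section 3 says the sponsor intends to use the results in regulatory decisions. Patient-level data stay at the five sites, so a late correction would mean re-running the extraction at each of them.

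**Working it through.** The document gives no sample size, event count or expected rate for this row, so there is no figure to reproduce. The check compares code lists.

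**1. The two ways to read the cell.**

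| Reading | What counts as erosion | Result |
|---|---|---|
| Both lists count | General device codes, vaginal-mesh codes, transfusion, infection, retention | Non-erosion events are recorded as erosion |
| Only the first list counts | 12 ICD-9 codes and 11 ICD-10 entries (10 distinct, T85.79XA appears twice) | 629.31/T83.711 and 629.32/T83.721S, the only codes labelled vaginal-mesh erosion or exposure, are lost |

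Neither reading is a valid definition.

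**2. Urethral-mesh codes.** The T83.712 and T83.722 families (bare code and A, D, S suffixes) have no code in common with the ICD-10 entries of the Mesh Erosion row. They are also missing from the mesh exposure and erosion subtype of the Re-Operation row, which lists 629.31, 629.32/T83.711 and T83.721.

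**3. Other conflicts in the row.**
- T83.721 appears only as T83.721S. The Organ Mesh Perforation row uses the S suffix for sequela. The re-operation subtype and the later surgical complications list give T83.721 without a suffix.
- Retention is paired as 778.2/R33.9 here and in the later list. The Voiding symptoms row pairs 788.20/R33.9, and the Re-Operation row uses 788.20 and 788.21. If records carry the 788.2x codes, retention enters the erosion row under ICD-10 but not under ICD-9, which makes an artificial step at the coding change.
- R33.9 is also in Voiding symptoms, and 996.69/T85.79XA is also in Surgical Site Infection. One coded event can count under two outcomes.

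**4. Can the error be sized?** Section 1.1 gives erosion requiring intervention at e = 1.6%, and voiding dysfunction at v = 3–30% (retropubic) and 0–16% (transobturator). The share s of voiding dysfunction that would carry R33.9 is not given; assume 10% to 100%. With erosion and retention independent (also assumed), the row flags 1 − (1 − e)(1 − v·s).
- v = 0: 1.6% flagged, all of it erosion.
- v = 3%, s = 10%: 1 − 0.984 × 0.997 = 1.9% flagged, of which 84% is erosion.
- v = 30%, s = 100%: 1 − 0.984 × 0.70 = 31.1% flagged, of which 5% is erosion.

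For missed cases, suppose a share u of erosions is coded only to T83.712 or T83.722 (assumed 10% to 50%). The captured rate is 1.6% × (1 − u), that is 1.44% down to 0.80%.

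A true-erosion share anywhere from 5% to 100% shows only that the document cannot size the error. Transfusion and infection have no rate at all.

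**The case against.** The strongest reply is that the sub-label separates the lists. Transfusion, infection and retention appear only under Surgical Complications, and that list largely repeats a generic one near the end of the appendix. The cell may have been meant as an erosion list with a complications list appended. This stands to the extent that the protocol nowhere states as a rule that a transfusion is an erosion. It does not rescue the row, because the most specific erosion codes sit under the same label.

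Second, the urethral codes are not lost to the protocol. They are collected as a dated outcome, and reporting urinary-tract erosion separately could be a deliberate choice. General codes such as T83.89XA or T83.9 might also catch some of these cases. This stands, and it limits the omission to the erosion row and the re-operation subtype. The protocol does not state how the two outcomes relate.

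Third, the re-operation subtype has a cleaner list. But it describes only erosions that led to re-operation, and it too omits the urethral codes.

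Fourth, each site reviews 50 to 100 charts, and the curated Mayo series offers a further check (Section 6). These may reveal misclassification, but they cover a subset of variables still to be chosen and do not define the outcome.

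Finally, the table is visibly a working list with open questions, and the note on 629.3x asks about exclusion without deciding it. That is fair, but the questions need closing before rates are produced.

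**Conclusion.** The point holds as a defect of definition. The Mesh Erosion row does not separate erosion codes from general surgical complications, and it omits the codes labelled urethral-mesh erosion or exposure. Applied literally it can misclassify in both directions, including in women without mesh. This rests on the code labels printed in the appendix and on the absence of any rule selecting among them.

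Three stronger readings are not supported. A reader might infer that the study's main result is spoiled, but Section 7 does not make erosion a primary outcome; the mismatch with Aim 2 is a separate matter to reconcile. A reader might infer that the resulting rate would mostly reflect events other than erosion, using the background rates in Section 1.1. That treats all voiding dysfunction as if it carried one retention code and assumes how retention and erosion overlap, and the document settles neither. A reader might also infer that the plan has decided to drop 629.31 and 629.32; the note only asks.

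**What to change.** In the Mesh Erosion row:
- Remove the transfusion (V58.2/30233N1, 30233P1, 30233H1), postoperative infection (998.5/T81.4x, T83.5, T83.6) and urinary retention (778.2/R33.9) codes.
- Keep 629.31, 629.32, T83.711 and T83.721 with all encounter suffixes, and close the note on 629.3x by retaining them.
- Count T83.712x and T83.722x as erosion. Either state that Organ Mesh Perforation is a subset of erosion or move the codes, so that one event is not reported as two separate outcomes. State the overlap of 996.69/T85.79XA with Surgical Site Infection in the same way.
- Keep the listed general device codes for dates before the 629.3x codes existed, and report erosion with and without the general codes over the whole period.

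Reconcile Aim 2, which names mesh erosion, with Section 7, which does not.

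The cost is one code-list edit, a sentence on how the outcomes relate, and a change to Section 7 or Aim 2. The drawback is that in the earliest ICD-9 period erosion rests on general device codes and is less specific; the paired reporting makes that visible.
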